1.3 SCHEDULE OF ACTIVITIES (SoA)

Table 1 Schedule of Activities (Subjects with Neurodegenerative Diseases, All Dose Cohorts)

Study Procedures	Screening ¹	Treatment	Follow-up	Notes
Study Visit	-42 to -1	Day 1	Day 8/EOS/ET	
Visit window (days)	42		+2	
Informed consent	X			
Domiciled		X ^a		a. Subjects will be admitted to the clinical research unit in the morning for 8 hours confinement
Medical/ocular history/Physical exam	X			On Day 1, PE may be repeated if abnormalities are detected at screening. Relevant ocular and disease-specific history will be captured up to date of diagnosis.
Eligibility (inclusion/exclusion criteria)	X			
Body weight and Height	X			
Eye examination/	X	X	X	Refer to Section 8.1.1.
Color fundus photography	X			
Vital signs	X	X ^b	X	b. To be collected predose, and at 0.25, 0.5, 1, 2, 8 hours postdose. A window of \pm 5 minutes will be allowed for measurements up to 2 hours, and \pm 10 minutes beyond 2 hours.
12-lead safety (ECG)	X	X ^c	X	c. Triplicate at the following timepoints: predose (within 1 hour), and at 90 minutes (\pm 15 minutes) and 8 hours (\pm 60 minutes) postdose or before discharge
Safety laboratories	X	X ^d	X	Refer to Section 10.2. d. To be collected predose on Day 1 and before discharge
Urinalysis	X	X	X	
Pregnancy test	S	U (predose)	U	S = Serum; U = Urine
Adverse event reporting	X	X	X	

Study Procedures	Screening ¹	Treatment	Follow-up	Notes
Study Visit	-42 to -1	Day 1	Day 8/EOS/ET	
Visit window (days)	42		+2	
Concomitant medications	X	X	X	
Retinal fundus fluorescence (FF) imaging		X ^e	X	e. Refer to Section 8.1.2
Retinal optical coherence tomography (OCT) and OCT angiography (OCTA)	X		X	
Blood PK sampling		X ^f		f. On Day 1, PK blood samples will be collected at the following time points: 0 (predose), and at 3, 6, 15, and 30 minutes postdose and 1, 2, 4, 6, and 8 hours postdose. A window of ± 5 minutes will be allowed for samples collected from 30 minutes to 2 hours, and ± 10 minutes beyond 2 hours.
Study drug administration		X		

Abbreviations: AE, adverse events; ECG, electrocardiogram; EOS, end of study; ET, early termination; FU, follow-up; PE, physical examination; PK, pharmacokinetics.

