4.3 JUSTIFICATION FOR DOSE

The proposed starting dose is based on recommendations from an FDA Guidance for Industry: *Estimating the Maximum Safe Starting Dose in Initial Clinical Trials for Therapeutics in Adult Healthy Volunteers, July 2005* (FDA, July 2005). Table 4 shows NOAEL doses and systemic AUC and C_{max} exposures from the pivotal rat and dog toxicity studies, as well as projected human exposures at proposed clinical dose levels. Clinical PK parameters (clearance and volume of distribution) for AMDX-2011P were projected by model fitting of dog PK data, then scaling to human values. AMDX-2011 parameters were projected based on rates of formation and

observed metabolite/parent ratios in animals. Human PK profiles were then simulated at various doses based on projected parameter values.

The lowest NOAEL for dogs (20 mg/kg, males) equates to a human equivalent dose (HED) for a 60-kg adult male of 667 mg, and the NOAEL for systemic toxicity in rats (50 mg/kg) equates to a HED of 484 mg. Using an ~20-fold safety margin, the starting dose in the proposed clinical study will be 25 mg. The escalating doses will be 25 mg, 50 mg, 100 mg, and either 150 mg or 200 mg.

The doses proposed for this study will cover the anticipated pharmacologically active dose range and are predicted to be significantly below AUC and C_{max} exposures for AMDX-2011 and AMDX-2011P achieved at NOAEL doses in rats and dogs.

Table 4 Projected Human Dose Levels and Corresponding AUC and C_{max} Exposures Based on Nonclinical Data

Dose	AUC (hr •ng /mL)		C_{max} (ng/mL)	
	AMDX-2011P^a	AMDX-2011^a	AMDX-2011P^a	AMDX-2011^a
Human (mg)				
25	49.0	19.1	135	43.8
50	97.8	38.2	269	87.5
75	144	57.4	403	131
100	192	76.6	539	175
150	288	115	806	263
200	383	153	1070	350
Dog NOAEL^b				
20 mg/kg (Male) (HED 667 mg)	400	182	2270	937
60 mg/kg (Female) (HED 2000 mg)	13,700	2200	45,500	5930
Rat NOAEL^c				
15 mg/kg (injection site reaction) (HED 145 mg)	923	138	7,175	1,019
50 mg/kg (Systemic) (HED 484 mg)	17,900	1,345	141,500	8,930

^a human AUC and C_{max} values are estimated from projected PK at each dose level

^b NOAEL in dogs based on ophthalmic clinical observations at 60 mg/kg in males and no adverse toxicity in females. AUC values are AUC_{last}

^c NOAEL in rats based on adverse injection site reactions at 50 mg/kg, but no adverse target organ (systemic) toxicity at up to 50 mg/kg. AUC_{last} and C_{max} are means of male and female values.

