8.3 PHARMACOKINETIC ASSESSMENT

Blood samples for determination of plasma concentrations of AMDX-2011P and AMDX-2011 will be collected as detailed in the SoA (Section 1.3). The timings of sample collection may be amended during the study conduct on the basis of emerging data to allow optimal characterization of the PK profile of AMDX-2011P and AMDX-2011.

Plasma concentrations of AMDX-2011P and AMDX-2011 will be measured by a specific and validated liquid chromatography-tandem mass spectroscopy (LC-MS/MS) method.

The following pharmacokinetic parameters (where appropriate) will be calculated by noncompartmental analysis from plasma concentrations of AMDX-2011P and for AMDX-2011 as defined in [Table 6](#).

Table 6 Pharmacokinetic Parameters

Parameter	Definition
C ₀	Back-extrapolated concentration at time = 0 hr (AMDX-2011P only)
C _{max}	Maximum observed drug concentration
T _{max}	Time of the maximum drug concentration
AUC _{0-last}	Area under the drug concentration-time curve from time zero to the last measurable concentration
AUC _(inf)	Area under the drug concentration-time curve from time zero to infinity
AUC _(0-t)	Area under the drug concentration-time curve from time zero to time t
t _{1/2}	Apparent terminal half-life
λ _Z	Apparent terminal elimination rate constant
CL	Systemic clearance (AMDX-2011P only)

Parameter	Definition
V _{ss}	Steady-state volume of distribution (AMDX-2011P only)

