6.9 Pharmacokinetic Analysis

PK Data Reporting and BLQ Imputation:

Individual plasma concentration data will be listed and summarized by cohort and dose levels / nominal time point with descriptive statistics (sample size [N], arithmetic mean, standard deviation [SD], median, minimum, maximum, geometric mean, and percent coefficient of variation [CV%]). Only concentration data collected within window of the scheduled timepoint will be included in summary tables and figures, however all data will be provided in data listings. Individual concentration data and descriptive statistics will be presented to 3 significant figures, except N, which will be reported as whole number CV% will be reported to one decimal place. For the purpose of descriptive statistics on the plasma concentration values and for PK analysis, all non-numerical values reported as being below the lower limit of quantification (BLQ) will be imputed as follows:

- Any BLQ value will be presented as 'BLQ' in the concentration table listings and footnoted accordingly.
- Any BLQ value prior to C_{max} will be set equal to zero. Any BLQ post C_{max} will be kept as "BLQ" and treated as a non-numerical value and excluded from descriptive statistics and PK analysis.
- In the event that two BLQ values are followed by a value within the quantification limit, the quantifiable value may be excluded from the analysis.

PK Parameter Estimation:

The PK parameters will be estimated by non-compartmental analysis (NCA) using Phoenix WinNonlin (v8.3 or later) using the data imputations described above. Actual sampling time points relative to dosing will be used for the NCA. There will be no imputation for missing data. No formal "outlier" analysis is planned. A profile must include at least consecutive quantifiable concentrations to be included in PK analysis. Subject profiles that are excluded from PK analysis (e.g. missing more than 2 samples, etc.) will be included in the concentration tables only and the reason for exclusion will be provided in the PK report.

Peak plasma concentrations (C_{max}) post dose administration and the corresponding T_{max} will be determined by direct assessment (no calculations) of the concentration vs time data.

All AUC calculations will be performed using the linear trapezoidal rule.

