If the data permit, the terminal rate constant (λz) will be calculated. The value of λz will be determined by the slope of the regression line of the natural log transformed concentrations vs time with the following constraints:

1. At least 3 data points post the C_{max} should be used in the regression; and
2. The correlation coefficient (R^2) of regression should be > 0.80 .

To optimize the reliability of the identified terminal phase (λz), where possible, the data points used to define the λz will be manually selected. The λz profiles that do not meet the guidelines stated above will not report the AUC_{INF} , $t_{1/2}$, CL or Vz parameters for that subject profile.

When possible, AUC_{INF} will be calculated as: $AUC_{last} + (C_{last} / \lambda z)$. CL will be calculated as: $Dose / (AUC_{INF})$ and Vz will be calculated as: $Dose / (AUC_{INF} * \lambda z)$. Terminal half-life ($t_{1/2}$) will be calculated as: $\log_e(2) / \lambda z$. If the lambda z range is not at least 2-fold greater than the calculated half-life value, the half-life value will be flagged and excluded from summary descriptive statistics.

If there any deviations from the planned treatment, then the analysis model specified or methods of analysis may be re-evaluated, as appropriate. Details of any deviations from the planned analysis will be documented in the PK report.

Individual subject PK parameters will be listed and summarized by cohort / dose levels with descriptive statistics (e.g. N, arithmetic mean, SD, median, minimum, maximum, geometric mean and CV%).

Individual parameters and descriptive statistics will be presented to 3 significant figures, except N, which will be reported as whole number, while individual T_{max} and half-life values will be reported to two significant figures.

PK Figures:

Mean \pm SD Concentration vs nominal time profiles will be generated on log/linear scales by cohort.

Overlay plots of all individual plasma concentration by actual time (or nominal time) for each cohort will be generated on log/linear axis, with each subject data represented with a different symbol and included in a legend. Individual subject concentration by time plots will also be produced on log/linear axis.

Mean \pm SD AUC_{last} versus dose plots will also be generated to assess dose proportionality / linearity.

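### The only output designated for dose proportionality is a plot of mean AUClast against dose, which can be biased upward if the last quantifiable time rises with dose and which gives no slope or interval

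*SAP*

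**What the plan says.** In SAP 6.9, under PK Figures, mean ± SD AUClast "versus dose plots will also be generated to assess dose proportionality / linearity". Neither document gives a dose-exposure model, a dose-normalised display or a criterion for proportionality.

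Four other provisions determine how AUClast behaves:

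- Protocol 8.3 (Table 6) defines it as the "Area under the drug concentration-time curve from time zero to the last measurable concentration", so its end time is set by each profile.
- SAP 6.9 keeps BLQ values after Cmax as BLQ, "treated as a non-numerical value and excluded from descriptive statistics and PK analysis".
- SAP 6.9 also states: "All AUC calculations will be performed using the linear trapezoidal rule".
- Protocol 1.3 samples at "0 (predose), and at 3, 6, 15, and 30 minutes postdose and 1, 2, 4, 6, and 8 hours postdose".

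The dose range is wide. Protocol 4.3 states: "The escalating doses will be 25 mg, 50 mg, 100 mg, and either 150 mg or 200 mg".

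AUCinf, AUC(0-t), Cmax and clearance are also derived (SAP 5.3 and 6.9) and summarised by cohort and dose level. None of them is assigned to proportionality, and t in AUC(0-t) is not fixed.

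**The concern.** With a fixed LLOQ, a low-dose profile can fall below the limit one or more sampling times before a high-dose profile. AUClast then covers a shorter interval at 25 mg than at 200 mg, and the missing area looks like a departure from proportionality. The late samples are 1 to 2 hours apart, so losing one sample removes a whole interval. The linear rule overstates the area of such an interval on a steeply falling curve, which widens the gap between doses that keep it and doses that lose it.

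Separately, a mean ± SD plot shows spread but does not estimate how exposure changes with dose or how well that change is known. The two lowest cohorts have only 3–9 subjects each, so this matters whatever the LLOQ.

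At stake is the description of exposure across an up to 8-fold dose range, and any extrapolation from it. Protocol 4.1 allows intermediate or higher dose levels to be explored.

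**Working it through.** **1. The plan's own projections.** The Table 4 rows (dose; AUC of AMDX-2011P and AMDX-2011; Cmax of each) are "25 49.0 19.1 135 43.8" and "200 383 153 1070 350". Scaling AUC by 200/25 = 8 gives 8 × 49.0 = 392 against 383, and 8 × 19.1 = 152.8 against 153. Log-log slopes over the six tabulated doses are 0.988 and 1.001. The protocol therefore projects essentially linear kinetics, and a method used to check this should return a ratio near 8.

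**2. Assumptions.** Table 4 gives no half-lives. Under one compartment, rate = Cmax/AUC:

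- AMDX-2011P: 135/49.0 = 2.76 per hour, half-life 0.693/2.76 = 0.25 h.
- AMDX-2011: 43.8/19.1 = 2.29 per hour, half-life 0.30 h, with an assumed formation rate of 30 per hour.

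I also assumed instantaneous injection, exact linearity, no noise, the protocol sampling times, the linear trapezoid, and BLQ values after Cmax dropped. LLOQ was varied from 0.05 to 5 ng/mL.

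**3. One case in full: AMDX-2011P, LLOQ 1.** At 25 mg, C(t) = 135·exp(−2.755t). This gives 135, 117.6, 102.5, 67.8, 34.0, 8.59 and 0.546 ng/mL at 0, 3, 6, 15 and 30 min, 1 h and 2 h.

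- 25 mg: the 2 h value is below 1, so AUClast ends at 1 h. The trapezoids are 6.32 + 5.50 + 12.77 + 12.73 + 10.66 = 47.98, and 47.98/49.0 = 0.979 of the true AUC.
- 200 mg: the 2 h value is 8 × 0.546 = 4.37, so AUClast ends at 2 h. Per 25 mg the extra trapezoid is (8.59 + 0.546)/2 = 4.57, where the true area is (8.59 − 0.546)/2.755 = 2.92. The sum is 52.55, or 1.072 of the true AUC.
- Ratio: 8 × 1.072/0.979 = 8.76.

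For AMDX-2011 the fractions are 0.906 (ending at 1 h) and 1.044 (ending at 2 h), so the ratio is 8 × 1.044/0.906 = 9.22. Without a formation phase it is 9.09.

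**4. Range.** The table gives the 200:25 mg AUClast ratio; the true value is 8.00. The slow-phase column puts 20% or 40% of AUC in a 2 h half-life, or 30% in a 4 h half-life (all assumed).

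| LLOQ, ng/mL | AMDX-2011P, one compartment | AMDX-2011, one compartment | Slow phase, both analytes |
|---|---|---|---|
| ≤0.1 | 8.00 | 8.00 | 8.00–8.10 |
| 0.2 | 8.00 | 8.00 | 8.00–8.31 |
| 0.5 | 8.00 | 9.22 | 8.00–8.97 |
| 1 | 8.76 | 9.22 | 8.65–9.94 |
| 2 | 8.76 | 9.22 | 8.73–12.2 |
| 5 | 8.00 | 11.2 | 9.68–16.9 |

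No scenario fell below 8. The ratio was exactly 8 whenever the last quantifiable time was the same at 25 and 200 mg. At LLOQ 5 the slow-phase values for AMDX-2011 alone run from 13.7 to 16.9.

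**5. What a fitted slope would deliver.** In a regression of ln(exposure) on ln(dose), SE = s/√Sxx with s = √ln(1 + CV²). That gives s = 0.294 at CV 30% and 0.472 at CV 50% (both assumed). For doses 25, 50, 100 and 200 mg, Sxx is 19.70 with 6, 6, 12 and 12 subjects and 12.83 with 3, 3, 12 and 12.

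- Best case: 0.294/√19.70 = 0.066, 90% half-width 1.645 × 0.066 = 0.11.
- Worst case: 0.472/√12.83 = 0.132, 90% half-width 0.22.

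**6. Candidate measures.** AUC over a common interval quantifiable at every dose gives exactly 8.00. AUCinf under the planned linear rule gives 8.26 (AMDX-2011P) and 8.31 (AMDX-2011) at LLOQ 1 with one compartment, and up to 9.85 with a slow phase. At LLOQ 5 with the formation phase, AMDX-2011 at 25 mg has only two points after Cmax. SAP 6.9 requires three for λz, so AUCinf would not be reported.

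**The case against.** A reader might infer that the plot cannot assess proportionality at all, or that it will look more than proportional. The documents do not support either reading. The LLOQ is unstated, Table 4 reports no half-life or terminal phase, and over part of the plausible range the artefact is nil. No single percentage can be given as its size.

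In the milder cases the bias is also small against the noise. The one-compartment slopes at LLOQ 1, fitted over the four doses, are 1.04 and 1.08, and the slope's own 90% half-width is 0.11–0.22. This stands for those cases. It does not stand for the slow-phase cases, where the slope reaches 1.20 at LLOQ 2 and 1.36 at LLOQ 5.

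The plot is not the only relevant information. AUCinf, Cmax and clearance are summarised by dose, and clearance is dose divided by AUCinf, which is a dose-normalised check. BLQ values appear in the listings, so truncation would be visible to someone who looked. This is a fair point, but none of these outputs is designated for the question, and Protocol Table 6 limits clearance to AMDX-2011P, leaving out the active moiety.

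Finally, SAP 6 rules out formal tests and inference, and the protocol sets no proportionality hypothesis. That is a good reason not to add a test or a margin. It does not argue against an estimate with an interval, because the same section allows 90% confidence intervals where appropriate.

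**Conclusion.** The point holds in conditional form and is a low-cost improvement, not a flaw that threatens the study. AUClast is a weak choice as the sole designated measure because nothing holds its end time constant across doses, and any resulting bias under linear kinetics is upward. With one-compartment half-lives inferred from Table 4, the apparent 200:25 mg ratio runs from 8.0 (no bias) to about 11, depending on LLOQ and analyte. Assumed slow phases extend this to about 12 at LLOQ 2 and about 15 (13.7 to 16.9) for AMDX-2011 at LLOQ 5. These figures rest on assumed LLOQs and disposition and are not predictions. If the top dose is 150 mg, the true ratio is 150/25 = 6 and the same mechanism applies over a narrower range.

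The lack of any slope or interval does not depend on these assumptions.

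**What to change.** For each analyte, regress ln(exposure) on ln(dose) and report the slope with a 90% CI, as description only. Use three measures:

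- Cmax;
- AUC(0-t) over one common interval that is quantifiable at every dose, with the rule for choosing t written into the SAP;
- AUCinf where λz can be estimated.

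Replace the mean ± SD AUClast figure with dose-normalised individual values. Tabulate last quantifiable time and percentage of AUC extrapolated by dose, and state the LLOQ for each analyte.

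The cost is a few lines of SAP text and a little more programming, with no new samples. There are two limitations. The common t is set by the lowest dose: in the case worked above it would be 1 h, covering 1 − exp(−2.755) = 94% of AMDX-2011P exposure, and less if there is a slow phase. AUCinf will be missing for some low-dose profiles, so it should not stand alone; otherwise dose-dependent truncation is simply exchanged for dose-dependent missing values.

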6.10 Exploratory Analyses

The following endpoints will be considered in the exploratory analysis, to be performed at the time of final analysis.

- time to clearance of all puncta,
- determining the residence time, defined as the time of injection to complete resolution of all identified puncta
- the number of post-injection spots
- distribution and total area of hyperfluorescent between cohorts
- peripheral puncta vs central, estimated number and size within the Macula and outside of the macula as reported by the grading center
- relationship between puncta and blood concentrations and residence time,

- time to maximum number of puncta detected

6.11 Other Assessments

6.11.1 ALS/Parkinson's/CAA Disease History

Disease history assessment will capture diagnostic criteria for each disease and also describes disease state for each subject.

- ALS Diagnostic Criteria
 - 1 - Definite ALS
 - 2 - Probable ALS
 - 3 - Probable ALS w/ Lab Result Supported
 - 4 - Possible ALS
- ALSRFS-R Score (0-10)
- Parkinson MDS Diagnostic Criteria:
 - 1 – Bradykinesia
 - 2 – Rigidity
 - 3 – Resting Tremor
 - 4 – Positive response to dopaminergic therapy
 - 5 – Levodopa – induced Dyskinesia
 - 6 – Documentation of resting tremor of a limb
 - 7 – Positive diagnostic test for olfactory loss
 - 8 – Positive diagnostic test of cardiac sympathetic denervation on scintigraphy
- Hoehn and Yahr Scale for Parkinson's subjects
 - 1 – Unilateral only
 - 2 – Bilateral or midline without impairment of balance
 - 3 – Bilateral
 - 4 – Severely disabling
 - 5 – Confinement
- MSA Diagnostic Criteria
 - Established MSA
 - MSA-C – Atrophy of: Putamen (and signal decrease on iron-sensitive sequences), infratentorial structures (pons and middle cerebellar peduncle). Hot cross bun sign.
 - MSA-P – Atrophy of Putamen (and signal decrease on iron-sensitive sequences), middle cerebellar peduncle, pons, and cerebellum. Hot cross bun sign.
 - Probable MSA
 - MSA-C – Atrophy of: Putamen (and signal decrease on iron-sensitive sequences), infratentorial structures (pons and middle cerebellar peduncle). Hot cross bun sign.
 - MSA-P – Atrophy of Putamen (and signal decrease on iron-sensitive sequences), middle cerebellar peduncle, pons, and cerebellum. Hot cross bun sign.
- CAA Diagnostic Criteria
 - 1 – Definite CAA
 - 2 – Probable CAA with evidence
 - 3 – Probable CAA
 - 4 – Possible CAA

6.11.2 Ophthalmoscopy

Measurements will be taken of the vitreous, macula, peripheral retina, choroid, optic nerve for both eyes and assessed on a scale of normal, abnormal (NCS), abnormal (CS), and not done.

6.11.3 Slit Lamp Biomicroscopy

Measurements will be taken of the subject's lids/lashes, conjunctiva/sclera, iris/pupil, cornea, anterior chamber, and lens at each protocol specified timepoint for both eyes and assessed on a scale of normal, abnormal (NCS), abnormal (CS), and not done.

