9.3.2 Safety Analyses

Continuous safety data will be summarized with descriptive statistics (arithmetic mean, standard deviation [SD], median, minimum, and maximum) overall, by treatment, and by nominal visit/time point (where applicable).

Categorical safety data will be summarized with frequency counts and percentages overall and within dose level. Adverse events will be coded by system organ class and preferred term using the most current Medical Dictionary for Regulatory Activities (MedDRA) version available. The number of subjects experiencing treatment-emergent adverse events as well as maximum severity and relationship to study drug will be summarized.

Laboratory evaluations, vital signs assessments, and ECG parameters will be summarized at protocol-specified collection time point. A summary of change-from-baseline at each protocol-specified time point will also be presented.

Concomitant medications will be listed by subject and coded using the most current World Health Organization drug dictionary.

Medical history will be listed by subject and coded using MedDRA.

Further details will be provided in the SAP.

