6 STATISTICAL ANALYSIS METHODS

No formal statistical tests or inference will be performed. All summaries will be presented using descriptive statistics for each cohort, and overall. Data processing, summarization, and analyses will be performed using SAS Version 9.4 or higher. Unless otherwise discussed, continuous variables will be summarized by the number of available data points (N), mean, standard deviation, median, minimum, and maximum. 90% confidence intervals, least-square means, and ratio for geometrics LS means will be displayed when appropriate. The mean, median, minimum, and maximum will be displayed with the same number of decimals as raw data, and the standard deviation will be displayed with two more decimals than raw data. Categorical variables will be summarized by the number and percentage of subjects in each level, where the denominator for each percentage is the number of subjects in the relevant population and specified cohort. Percentages will be displayed to one decimal place and proportions will be displayed to three decimal places. Data listings of all data collected on the eCRF will be presented, sorted by subject number and visit, where applicable.

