6.7 Primary (Safety) Analysis

The primary analysis for this study will assess the safety of study drug, AMDX-2011P. Adverse Events will be coded by System Organ Class and Preferred Term using MedDRA, Version 25.0. The number and percentage of subjects experiencing treatment-emergent adverse events, serious adverse events, maximum severity to study drug, and highest relationship to study drug will be summarized by cohort and listed by subject ID for both eyes. Treatment emergent adverse events and serious adverse events leading to discontinuation will also be presented by count. Treatment emergent adverse events are defined as any AEs with an onset date on or after the date of the first dose of the investigational product or is pre-existing and worsens after administration. TEAEs severity will be measured by the severity scale: mild, moderate, severe, life-threatening, and fatal. The degree of certainty of causality will be graded using the following categories: definite, probable, possible, unlikely, and not related. A line listing of all treatment emergent adverse events will be provided including as reported verbatim term, SOC, PT, onset date, end date, severity, seriousness, causality, dose level, outcome and action taken with investigational product. Subjects with 1 or more than one TEAE per system organ class and preferred term will be counted once and be reported with the highest severity. In cases where severity or relationship are missing, the most conservative approach will be taken (i.e., highest severity and assumed to be related). Laboratory evaluations, vital sign assessments, and ECG parameters will be summarized using appropriate statistics at protocol-specified time points, as well as change-from-baseline at all protocol-specified post-baseline timepoints. Non-ocular adverse events will be summarized separately and listed by subject ID for both eyes.

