6.7.5 Intraocular Pressure

Intraocular pressure (mmHG) using contact or non-contact tonometry will be assessed and summarized for both eyes for each protocol specified timepoint.

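### Planned eye-examination tables summarise each visit separately, so in general they cannot tell new or worsened findings from pre-existing ones

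*SAP*

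**What the plan says.** SAP 6.7 assigns change from baseline to three data types: "Laboratory evaluations, vital sign assessments, and ECG parameters will be summarized using appropriate statistics at protocol-specified time points, as well as change-from-baseline". SAP 6.7.1 adds baseline-referenced categories for ECG. In Protocol 9.3.2 the corresponding sentence, "A summary of change-from-baseline at each protocol-specified time point will also be presented", directly follows a sentence on the same three data types.

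The eye examination is treated differently:

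- IOP (SAP 6.7.5) "will be assessed and summarized for both eyes for each protocol specified timepoint".
- Ophthalmoscopy (SAP 6.11.2): "Measurements will be taken of the vitreous, macula, peripheral retina, choroid, optic nerve for both eyes", followed by a grading scale and no summary format.
- Slit lamp (SAP 6.11.3): structures are recorded "at each protocol specified timepoint for both eyes and assessed on a scale of normal, abnormal (NCS), abnormal (CS), and not done", again with no summary format.
- Visual acuity is part of the examination in Protocol 8.1.1 but has no SAP section.

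Two defaults in SAP Section 6 fill part of the gap. For tables, "Categorical variables will be summarized by the number and percentage of subjects in each level". For listings, "Data listings of all data collected on the eCRF will be presented, sorted by subject number and visit, where applicable". Protocol 9.3.2 likewise commits to counts and percentages of categorical safety data within dose level, and to summaries of continuous safety data by treatment and nominal visit.

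**The concern.** Protocol 8.2 lists the ophthalmologic examination among the safety assessments. Table 2 in Protocol 2.3.1 gives it as the mitigation for the potential effect on the eye and as part of the mitigation for phototoxicity. The male-dog no-observed-adverse-effect level was set by eye signs.

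The examination is scheduled at screening, Day 1 and Day 8, and Protocol 4.1 places the Day 1 examination before dosing. Paired predose and post-dose data are therefore collected, but no planned table uses the pairing. At stake is supporting safety information by dose: shifts from normal to the lower abnormal grade (NCS), and changes in IOP or acuity, that the investigator does not report as adverse events.

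**Working it through.** The plan states no figure on this point, so there is none to reproduce. The check is what visit-by-visit tables can reveal about change within subjects.

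**Inputs.** Cohort sizes are 3 to 9 (cohorts 1 and 2) and 12 (cohorts 3 and 4), from Protocol Table 3. There are 6 slit-lamp structures (SAP 6.11.3) and 5 ophthalmoscopy structures (SAP 6.11.2). The analysis window for the Day 8 visit is Day 8 to 14 (SAP 3.3). The documents give no predose abnormality rate, so the counts below are assumed illustrations. Complete pairs are also assumed.

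**1. One structure, one eye, normal or abnormal.** Let n be the cohort size, a the number abnormal predose, b the number abnormal at Day 8, and x the number newly abnormal. Then x cannot exceed b or n − a. The number abnormal at both visits, b − x, cannot exceed a. So

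max(0, b − a) ≤ x ≤ min(b, n − a).

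- n = 12, a = 3, b = 3: x is 0 to 3 (0 to 25.0%).
- n = 12, a = 3, b = 4: x is 1 to 4 (8.3 to 33.3%).
- n = 3, a = 1, b = 1: x is 0 or 1 (0 or 33.3%).
- a = 0: x = b exactly.

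The range closes only when nobody or everybody is abnormal at one of the two visits.

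**2. Three grades.** Take 8 normal, 3 NCS and 1 CS at both visits in 12 subjects. If nobody changed, 0 worsened. At the other extreme, all 3 NCS and the 1 CS at Day 8 came from a better grade, so 4 worsened. One table that gives this: 3 normals move to NCS, 1 NCS moves to CS, and 2 NCS and 1 CS move to normal, leaving 5 + 2 + 1 = 8 normal. The range is 0 to 4 of 12 (0 to 33.3%).

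**3. Subjects affected.** There are 6 + 5 = 11 structures and 11 × 2 = 22 structure-by-eye counts. Even with nobody abnormal predose, one new abnormality in each of 3 of these counts could be one subject or three: 1 to 3 of 12 (8.3 to 25.0%).

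**4. IOP.** With complete pairs, the mean change is the difference between the two visit means and can be read off. Its spread cannot. With equal visit SDs s and within-eye correlation r, SD of change = s × √(2(1 − r)). For an assumed r of 0.5 to 0.9 this runs from √1.0 = 1.00 s down to √0.2 = 0.45 s.

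**5. What is already covered.** The treatment-emergent definition in SAP 6.7 includes an event that "is pre-existing and worsens after administration", counted by cohort. Protocol 8.4.4 has deterioration of a condition present at screening recorded as an adverse event. Protocol 6.1.1 has subjects evaluated for phototoxicity. The before-and-after comparison of puncta in SAP 6.8 is an activity measure on fluorescence images and does not serve the safety examination. What remains is change below the adverse-event threshold.

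**The case against.** The strongest case on the other side has five parts.

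- **By-dose eye tables are already promised.** This stands. A reader might infer that the plan gives no eye-examination table by dose, but Protocol 9.3.2 and the SAP Section 6 defaults do not support that. The 9.3.2 commitment extends to visual acuity as safety data. Where no subject is abnormal predose, the planned count of new abnormalities per structure is exact, and exclusion criterion 5 should keep predose retinal abnormalities low.
- **Adverse-event rules catch what matters.** Largely true. Protocol 8.2.2 to 8.2.4 state explicitly that significant vital-sign, ECG and laboratory changes become adverse events, and 8.1.1 has no matching rule for eye findings. The general definition in 8.4.1 and the deterioration rule in 8.4.4 still apply. They do not clearly reach a shift from normal to NCS.
- **Listings and committee review suffice in small cohorts.** Partly true. Pairing 12 subjects by hand is feasible, and the Safety Monitoring Committee reviews all available safety data. A count by dose would still have to be built after the fact.
- **Day 8 is too late.** The dog signs appeared within 24 hours and reversed within 6 days. The post-dose examination falls 7 to 13 days after dosing (Day 8 − Day 1 = 7; Day 14 − Day 1 = 13). A Day 8 table would probably miss such signs and would show mainly persistent change. This limits the gain.
- **Full shift tables are excessive.** Agreed: 22 structure-by-eye grids for four dose levels plus overall make 22 × 5 = 110 grids, mostly sparse. The remedy should be more compact.

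**Conclusion.** The point holds in a limited form. The stated method gives margins by dose and visit. Except at the extremes, margins cannot separate pre-existing from new or worsened findings, and they give neither the number of subjects affected nor the spread of IOP change. The paired data needed for all three are already collected.

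The ranges in the working are exact bounds, but on assumed counts and an assumed correlation. They show what the tables could fail to distinguish and do not predict results in this trial.

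A reader might go further and conclude that eye toxicity would go unreported or that the primary safety analysis is compromised. The documents do not support that: findings reported as adverse events are tabulated by cohort, every eye-examination value on the eCRF is listed, and no escalation rule is shown to depend on the missing tables. This is an optional improvement to supporting tables.

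**What to change.** In SAP 6.7, add for the eye examination, by dose level and overall:

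- The number and percentage of subjects whose slit-lamp or ophthalmoscopy grade worsens from Day 1 predose to Day 8, by structure (worse eye) and for any structure in either eye. This is 11 + 1 = 12 rows.
- Per-eye change from Day 1 predose in IOP.
- Per-eye change from Day 1 predose in visual acuity, where collected, with a new SAP section that states the scale on which change is measured.

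Keep full three-by-three shift grids optional, or present them overall only. State that these tables supplement treatment-emergent adverse event reporting, because an examination on Day 8 to 14 may miss transient signs.

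The cost is SAP wording and a few descriptive tables, mostly sparse, from data already collected. No assessment is added, and the primary endpoint does not change.
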